#### 10.0 CRITERIA FOR EVALUATION AND ENDPOINT ANALYSIS

10.1 Measurable disease

For the purpose of measuring hematologic response, measurable disease is defined as:

a. Positive monoclonal serum immunofixation electrophoresis or urine immunofixation electrophoresis,

and/or

- b. Serum free light chain ratio outside of normal range (normal range: 0.25 1.65)
- 10.2 Hematologic Response and Progression

Confirmation must be made by verification on two consecutive determinations.

- a. Hematologic response: (16, 17)
  - Complete Response (CR): CR is defined as laboratory values within the normal range free light chain (FLC) ratio (0.25 – 1.65) and negative serum and urine immunofixation (as per institutional laboratory values).
  - Very Good Partial Response (VGPR): A VGPR is defined as the difference between involved and uninvolved FLCs [dFLC] < 4.0 mg/dL.

  - Partial Response (PR): Partial Response is defined as a dFLC decrease of ≥ 50%, but remaining > 4.0 mg/dL
- b. Hematologic progression: 50% increase from nadir, or from baseline (if there was no response) in any ONE OR MORE of the following: *(18)* 
  - 1. Serum M-protein: 50% increase in Serum M protein to a value greater than 0.5 g/dL.
  - 2. Urine M protein: 50% increase in Urine M protein to a value greater than 200 mg/day (a visible peak must be present)
  - 3. Free light chain increase of 50% to a value greater than 10 mg/dL
- c. Stable Disease: Patients who do not meet criteria for objective response or progression (see Sections 10.2a and 10.2b) will be termed to have stable disease.
- 10.3 Organ Response (19)

Response to therapy in terms of improvement in organ dysfunction will be defined based on functional improvement in one or more involved organ systems. Only 1 parameter is required to satisfy the organ response criteria. In order to be classified as a confirmed organ response, confirmation must be made by verification on a second consecutive assessment at least 4 weeks after the first observation of response.

- a. Liver response requires either:
  - 1. A 50% decrease in (or normalization of, <1.5 IULN) alkaline phosphatase level, or
  - 2. A reduction in the span of the liver by at least 2 cm by radiographic determination.
- b. Renal response is defined as either: (20)
  - 1. A 30% decrease in urine total albumin; or
  - 2. A decrease to less than 500 mg/24 hours urine total protein without renal progression (where renal progression is defined in Section 10.4a.1).
- c. Gastrointestinal response is defined as either:
  - 1. Reduction in 24-hour fecal fat excretion by  $\ge$  50% in patients with steatorrhea; or
  - 2.  $\geq$  50% reduction in number of loose stools per day in patients with diarrhea.
- d. Cardiac response is defined as either: (21)
  - NT-proBNP response (>30% decrease and at least 300 pg/mL decrease is needed from the baseline result if NT- proBNP > 650 pg/mL at baseline) or
  - 2. NYHA class decrease from 1 to 0; 2 to 1 or 0 or from 3 to 1 (2 class decrease if baseline NYHA III). (That is, If NYHA is 1 or 2, a 1-class level drop is required. If NYHA is a 3, a 2-class level drop is required.)
- e. A neurologic response is defined as:
  - 1. Clear improvement in neuropathy (peripheral or autonomic) in the opinion of the treating investigator. For peripheral neuropathy, the Neuropathy Impairment Tool Lower Limbs (NIS-LL) must be used to assess response.

The NIS (LL is a scoring system graduated from 0 points (the normal finding) to a maximum of 88 points (the absence of all motor, sensory, and reflex activity in the lower extremities). The scale is additive of all deficits (64 potential points for muscle strength, 8 points for reflexes, and 16 points for sensory function) in the lower extremities. A NIS-LL score demonstrating a decrease from baseline of  $\geq$  2 points is indicative of organ response. (22)

See Section 18.2.

2. For autonomic neuropathy, a clear improvement in the opinion of the investigator including improvement in orthostatic blood pressure (systolic blood pressure (SBP)) readings and symptoms of dizziness and nausea on 2 separate occasions.

- a. Orthostatic hypotension is defined as a decrease in systolic blood pressure of 20 mm Hg or a decrease in diastolic blood pressure of 10 mm Hg within three minutes of standing when compared with blood pressure from the sitting or supine position. Orthostatic symptoms include dizziness, lightheadedness, nausea
- f. Soft tissue/lymph nodes: There is no reliable method for assessing soft tissue responses. Determination of soft tissue response will be performed by the site investigator in conjunction with the PI/Medical Monitor. Examples of soft tissue responses would include decreased size and thickness of tongue, or improved tongue mobility, on physical examination (for macroglossia); objective decrease in size of soft tissue deposits on examination or imaging.
- 10.4 Criteria for Organ Progression

Progression will be defined based on objective evidence of worsening of organ dysfunction due to AL amyloid.

- a. Any ONE of the following criteria must be met to be termed as organ progression for the purpose of this study:
  - 1. Renal: A 50% increase (at least 1 g/day) of 24-hour urine protein to > 1 g/day OR 25% worsening of serum creatinine or creatinine clearance (Cockcroft-Gault method).
  - 2. Hepatic progression is defined by either:
    - a. A 50% increase of alkaline phosphatase level above lowest level, or
    - b. An increase in liver span by at least 2 cm (radiographic determination).
  - 3. Gastrointestinal: Worsening of diarrhea with an increase 50% of previous movements per day (not attributable to the study drug or an alternative explanation in the opinion of the treating physician) or 24-hour fecal fat increase by 50%.
  - 4. Cardiac: An increase in cardiac wall thickness by 2 mm or an increase in NYHA class by one grade with a decreasing ejection fraction of 10%, or an increase in NT-proBNP by > 30% and >300 pg/mL or an increase in troponin T or I by ≥ 33%.
  - 5. Neurologic: Clearly progressive neuropathy (peripheral or autonomic) that in the opinion of the treating investigator is unrelated to study drug.
    - a. For peripheral neuropathy, the Neuropathy Impairment Tool Lower Limbs (NIS-LL) must be used to assess progression.

The NIS (LL is a scoring system graduated from 0 points (the normal finding) to a maximum of 88 points (the absence of all motor, sensory, and reflex activity in the lower extremities). The scale is additive of all deficits (64 potential points for muscle strength, 8 points for reflexes, and 16 points for sensory function) in the lower extremities. A NIS-LL score demonstrating an

increase from baseline of  $\geq$  2 points is indicative of organ progression. (23)

See Section 18.2.

- b. Clear worsening of orthostatic vital signs (SBP) and symptoms of dizziness or nausea on 2 separate occasions.
- 6. Soft tissue/lymph nodes: Clearly progressive macroglossia or symptomatic soft tissue deposits.
- 10.5 Time to Hematologic Response

From date of registration to date of first documentation of hematologic PR, VGPR, or CR as defined in Section 10.2.

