#### 2.3 Isatuximab

Isatuximab (SAR) is an IgG1k monoclonal antibody (mAb) that binds with high affinity to a unique epitope on CD38. It is a targeted immunotherapy that attacks tumor cells that overexpress CD38, a transmembrane glycoprotein, in a variety of hematological malignancies including plasma cell malignancies. Isatuximb induces lysis of CD38-expressing tumor cells, including malignant plasma cells by a wide spectrum of mechanisms including complement-dependent cytotoxicity (CDC) and antibody-dependent cell-mediated cytotoxicity (ADCC). The most common adverse reactions seen are infusion reactions that can be mitigated and managed with corticosteroids and antihistamines, both as prophylaxis and treatment.

Isatuximab has been shown to be efficacious and well tolerated in relapsed and refractory multiple myeloma patients when used as a single agent as well as in various combinations with other agents.

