#### Mechanism of Action:

Isatuximab is an immunoglobulin G1 monoclonal antibody that selectively binds to the human cell surface antigen molecule CD38 expressed in a number of hematological malignancies from B-lymphocyte, T-lymphocyte, and myeloid origin. The agent works through antibody-dependent cellular-mediated cytotoxicity,

complement-dependent cytotoxicity, antibody dependent cellular phagocytosis, and induction of apoptosis.

- b. PHARMACOKINETICS
  - Absorption: Exposure increased more than proportionally with the dose from 0.03 to 20 mg/kg. Some accumulation was observed following 10 or 20 mg/kg administered with qw or q2w schedule. Achievement of steady state has not been formally evaluated yet. Additionally, four doses of 20 mg/kg QW showed that total clearance (sum of nonlinear and linear clearances) approached linear clearance (indicating target saturation) after which the 20 mg Q2W schedule appeared to maintain the total clearance close to the linear clearance.

Isatuximab has a low clearance to those of non-specific endogenous IgG associated with a half-life of 18 days and the volume of distribution of central compartment (Vp) approached the blood volume. Because isatuximab is an antibody, it is expected to be eliminated by proteolytic catabolism.

- 2. Distribution: The PK of isatuximab appeared to be nonlinear in the dose range investigated in studies. More precisely, after the first administration, the exposure (AUC1week, AUC2weeks, or AUClast) appeared to increase more than proportionally with the dose up to 10 mg/kg, while no major deviation to the dose proportionality could be observed between 10 mg/kg and 20 mg/kg. This nonlinearity suggests the presence of target-mediated drug disposition with isatuximab.
- 3. Metabolism: No available data; being evaluated.
- 4. Elimination: Some accumulation was observed following 10 or 20 mg/kg administered with every-week or every-2-week schedule. Achievement of steady state has not been formally evaluated yet.

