#### Vital Sign Monitoring

Blood Pressure is collected at baseline. Vitals below will be performed per drug safety monitoring.

**First infusion:** Prior to infusion obtain vital signs (BP, HR, temp, oxygen saturation by pulse oximeter). Repeat every 15 minutes for the 1st hour, then every 30 minutes and with each rate change for the duration of the infusion and continue for 30 minutes after the end of the infusion.

**Second infusion:** Prior to infusion obtain vital signs (BP, HR, temp, oxygen saturation by pulse oximeter). Repeat every 30 minutes and with each rate change for the duration of the infusion and continue for 30 minutes after the end of the infusion

**Third and subsequent infusions:** Prior to infusion obtain vital signs (BP, HR, temp, oxygen saturation by pulse oximeter). Repeat every 30 minutes and with each rate change for the duration of infusion and at the end of infusion.

c. Potential Interference with Blood Bank Serologic Tests:

The CD38 protein is weakly expressed on the surface of red blood cells. Because of this, anti-CD38 antibodies in patients' plasma can lead to pan-reactivity and thus interfere with various blood bank serologic tests. To avoid potential problems with blood transfusion, the American Association of Blood Banks recommends that patients being treated with anti-CD38 antibodies have blood type and screen tests performed at baseline, after treatment, and each time before blood infusion.

Type and screen patients and notify institutional blood bank before the first administration of the drug and repeat prior to any blood product transfusion. RBC antigen screen is recommended but not required, as per institutional blood bank protocol, and a card with blood type will be carried by the patient throughout the study (see Appendix 18.6). Baseline type and cross should be used for transfusions, as post-treatment blood type does not change but appears different due to presence of the CD38 antibody.

d. Strongly recommend that blood pressure is controlled prior to beginning infusion on Day 1, Cycle 1, as per American Heart Association standards, preferable SBP ≤ 140 and DBP ≤ 90. Blood pressure must be SBP ≤ 160 and DBP ≤ 100 on Day 1 Cycle 1.

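### Complete response may be under-recorded, because it requires a negative serum immunofixation while the study drug is itself an IgG kappa monoclonal protein and no rule covers a drug band

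*Combined protocol and SAP*

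**What the plan says.** Section 10.2a of the protocol defines the three response categories:

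- **CR:** "CR is defined as laboratory values within the normal range free light chain (FLC) ratio" (0.25 to 1.65), together with "negative serum and urine immunofixation (as per institutional laboratory values".
- **VGPR:** "A VGPR is defined as the difference between involved and uninvolved FLCs [dFLC] < 4.0 mg/dL", with no immunofixation condition.
- **PR:** "Partial Response is defined as a dFLC decrease of ≥ 50%, but remaining > 4.0 mg/dL".

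Section 10.2 adds: "Confirmation must be made by verification on two consecutive determinations".

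On the drug, Section 2.3 states: "Isatuximab (SAR) is an IgG1k monoclonal antibody (mAb". Section 3.1b gives a "half-life of 18 days and the volume of distribution of central compartment (Vp) approached the blood volume". Section 7.3 schedules 20 mg/kg on Days 1, 8, 15 and 22 of Cycle 1, then on Days 1 and 15 of Cycles 2 to 24, with 28-day cycles.

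The Section 9.0 calendar has serum immunofixation at pre-study and in every treatment cycle. It has no entry in off-treatment follow-up before progression, whereas SPEP and serum FLC do.

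Section 7.1c and Appendix 18.6 recognise that anti-CD38 antibodies can "interfere with various blood bank serologic tests" and direct staff to the baseline result. Nothing comparable is written for immunofixation.

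**The concern.** Immunofixation identifies monoclonal immunoglobulin by isotype. A therapeutic IgG kappa antibody is one, so a patient whose own clone has gone and whose FLC ratio is normal could still show an IgG kappa band. Read literally, Section 10.2a then denies CR because of the treatment. Confirmation does not help, since consecutive on-treatment tests share the same exposure.

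The error runs in one direction, and it may differ by site. One laboratory may score only the original clone and another may report any band, and both would satisfy the reference to institutional laboratory values. At stake is the split of responders into CR, VGPR and PR. Section 2.1 itself treats CR as prognostically important: median OS was 13.2 years with CR and 5.9 years without it in the transplant series it cites. If the attribution of bands is decided only once results are known, it becomes an unplanned reclassification of response.

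**Working it through.** **1. The plan's own figure.** The design has 20 then 15 patients, continues with 2 or more responses, and succeeds with 8 or more of 35. The exact two-stage probability is the sum over x = 2 to 20 of P(X1 = x) × P(X2 ≥ max(0, 8 − x)). It gives 0.0199 at a 10% rate and 0.8664 at 30%, matching the stated 2% and 87%. Moving a patient from CR to VGPR leaves CR + VGPR + PR unchanged, so neither figure moves.

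**2. Drug remaining at a test (no volume needed).** The fraction left after t days is 2^(−t/18).
- 7 days (last Cycle 1 dose to Cycle 2 Day 1): 0.764.
- 14 days (Day 15 to the next Day 1): 0.583.

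**3. Serum level just before the Day 1 dose.** Assumptions: one compartment, linear clearance, sampling before dosing, and a volume V of 50 to 140 mL/kg. The documents say only that the central volume approached blood volume and give no mL/kg figure. Section 3.1b reports that the 20 mg/kg weekly-then-two-weekly schedule kept total clearance close to linear, which supports the simple model.

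Increment per dose = 20 mg/kg ÷ V. At 70 mL/kg this is 286 mg/L.
- Cycle 2 Day 1 = increment × (0.764 + 0.583 + 0.446 + 0.340) = increment × 2.133.
- Steady-state trough = increment × 0.583/(1 − 0.583) = increment × 1.40.

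| V (mL/kg) | Cycle 2 Day 1 (mg/L) | Steady-state trough (mg/L) |
|---|---|---|
| 50 | 853 | 560 |
| 70 | 609 | 400 |
| 100 | 427 | 280 |
| 140 | 305 | 200 |

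A 14-day cycle delay, which Section 8.3b permits, multiplies the trough by 0.583: 400 becomes 233 mg/L, and 200 becomes 117 mg/L.

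**4. Would it be seen?** The documents give no detection limit. For assumed limits of 50 to 150 mg/L, the undelayed trough is above the limit across the whole volume range. For 250 mg/L it is above only while V is below 20 × 1.40 × 1000/250 = 112 mL/kg; for 300 mg/L, below about 93 mL/kg. After the last dose, time above the limit = 18 × log2(steady-state peak/limit). At 70 mL/kg this is about 68, 50, 39 and 26 days for limits of 50, 100, 150 and 250 mg/L. No immunofixation is scheduled after that interval.

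**5. Patients affected.** If every drug band were visible and scored positive, recorded CRs would be zero. With assumed true CR rates of 5%, 10%, 20% and 30%, 35 × rate = 1.75, 3.5, 7 and 10.5 patients would be relabelled. If half were scored positive, half as many would be. As an illustration, 7 of 35 has an exact 95% interval of 8.4% to 36.9%, while 0 of 35 has an upper limit of 10.0%.

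**6. Where a denied CR lands.** Usually dFLC is below 4.0 mg/dL, which is VGPR. A normal ratio does not guarantee it. With a lambda clone, kappa 1.5 and lambda 6.0 mg/dL give a ratio of 0.25 and dFLC of 4.5. That is PR if baseline dFLC was at least 9.0 (a 50% fall), and otherwise stable disease. A dFLC of exactly 4.0 mg/dL fits neither the VGPR nor the PR definition.

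**The case against.** A reader might infer that true CRs will be recorded as VGPR, or that the recorded CR rate must approach zero. The documents do not support that. They give no immunofixation sensitivity and do not discuss whether isatuximab is visible on it. The interference they describe is confined to blood-bank serology. Section 10.2a leaves the reading to the institution, so a site could judge the band against the original clone, most easily when that clone is lambda or not IgG. At the larger volumes the trough falls below a 250 or 300 mg/L limit. The pre-study test, and Cycle 1 Day 1 if drawn before dosing, are drug-free, although neither can establish a CR. These points stand and limit the claim to what may happen.

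It is also fair that little formal inference depends on the split. CR rate is not an objective in Sections 1.1 to 1.3, and Section 11 plans no separate CR estimate. Time to response starts at any of PR, VGPR or CR. The highest predicted drug level, about 1.1 g/L (0.11 g/dL) after the fourth weekly dose at 50 mL/kg, is well under the 0.5 g/dL serum M-protein progression threshold, so the drug alone would not trigger it. The survival contrast in Section 2.1 comes from transplant recipients, whereas Section 5.2f admits patients who are ineligible for transplant or declined it.

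What remains is that the categories are defined separately, and the definition of the deepest one can fail because of the drug under study.

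**Conclusion.** The point holds in a limited form. The documents establish that CR needs a negative serum immunofixation, that drug is present at every scheduled post-dose test, that no post-washout test is scheduled, and that no rule covers a drug band. CR may therefore be under-recorded. How often depends on two unknowns, the assay's detection limit and how sites score the band, and on the assumed volume behind the 0.2 to 0.56 g/L trough. The count of 1.75 to 10.5 relabelled patients is a worst case over assumed true CR rates of 5% to 30%.

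A reader might also infer bias in the primary endpoint. The pooled response rate, the 2% and 87% figures and the 8-of-35 rule all stand, apart from rare patients with a normal ratio, dFLC of 4.0 mg/dL or more, and a fall that does not qualify as PR. The consequence is for reported depth of response. This is a cheap improvement; confidence is medium.

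**What to change.** Add to Section 10.2a:

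- When the FLC ratio is normal and urine immunofixation is negative, a sole serum IgG kappa band that was absent at baseline, in a patient whose baseline clone is not IgG kappa, is treated as possible drug interference and does not by itself exclude CR.
- If the baseline clone is IgG kappa, or the bands cannot be separated, record *CR not assessable* and classify the response by dFLC.

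Record the band isotype at each assessment, if the AL Follow Up Tumor Assessment Form does not already do so. In Section 11.3, state that the CR rate will be reported both with and without drug-attributed and not-assessable cases.

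The cost is a few sentences and possibly one form field. No new test is needed, because baseline and per-cycle serum immunofixation are already in the calendar. There are two downsides. Some patients become not assessable for CR, and a new, unrelated IgG kappa band could be wrongly attributed to the drug, which would over-count CR. Reporting the rate both ways makes the size of either effect visible.

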### 1.0 OBJECTIVES

#### 1.1 Primary Objective

To assess the efficacy as measured by the confirmed overall hematologic response rate (partial response or better) of isatuximab in relapsed/ refractory systemic light chain (AL) amyloidosis.

- 1.2 Secondary Objectives
  - a. To evaluate toxicities in the treatment of relapsed/ refractory AL amyloidosis with isatuximab.
  - b. To evaluate time to hematologic response.
  - c. To evaluate duration of response.
  - d. To evaluate progression-free survival (PFS).
  - e. To evaluate overall survival (OS).
- 1.3 Other Objectives
  - a. To evaluate efficacy of isatuximab in relapsed/ refractory immunoglobulin amyloid light chain (AL) amyloidosis as measured by organ specific response rates (cardiac, renal, GI, liver, soft tissue, nerve), in the subset of patients that can be evaluated for organ response.
  - b. To evaluate time to organ response in the subset of patients that can be evaluated for organ response.

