#### 11.0 STATISTICAL CONSIDERATIONS

11.1 Two-Stage Design

The primary goal of this study is to test the hypothesis that the rate of confirmed overall hematologic response (CR+VGPR+PR) to treatment is at most 10% versus the alternative that the true hematologic response rate is 30% or greater.

A two-stage design will be used for patient accrual, with a total of 35 eligible patients who are evaluable for hematologic response per the definition in Section 11.2b below. (24) Patients who received at least one dose of study drug will be considered evaluable. Initially, 20 eligible, evaluable patients will be accrued. If one or fewer hematologic partial or better responses are observed in the first 20 patients, this treatment will be considered insufficiently active in this population and further accrual will be terminated. If two or more confirmed, partial or better responses are observed, then an additional 15 eligible, evaluable patients will be accrued. If at least 8 out of the total 35 patients have a confirmed response, the treatment may be recommended for further testing in subsequent studies. An estimated 39 patients will be enrolled to this study (including 35 eligible and evaluable patients, with 20 enrolled to Stage 1 and 15 enrolled to Stage 2, and with an additional 4 patients enrolled overall to account for ineligible and unevaluable patients).

With an estimated accrual rate of 1-2 patients per month, it is anticipated that the study will reach full accrual in 20 to 40 months.

- 11.2 Sample size and Power Justification
  - a. Assuming the number of hematologic responses is binomially distributed this design has a significance level of 2% and a power of 87% for detecting a true overall hematologic response rate of at least 30% versus the null hypothesis response rate of 10% of less.
  - b. All eligible patients who receive any study treatment will be considered to be evaluable for response and toxicity, and will be included in the analysis.
  - c. Patients who go off study or die prior to the first response assessment will be considered as non-responders.
- 11.3 Analysis of Primary Endpoint

The primary endpoint of this study is overall confirmed hematologic response rate (ORR), which includes partial response (PR), very good partial response (VGPR) and complete response (CR) as defined in Section 10.2.

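### A dFLC of exactly 4.0 mg/dL after a fall of at least 50% is neither PR nor VGPR, so a deep fall counts as stable disease in a primary endpoint of PR or better

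*Combined protocol and SAP*

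**What the plan says.** The primary objective in Section 1.1 is the "confirmed overall hematologic response rate (partial response or better) of isatuximab". Section 11.3 describes the endpoint as one "which includes partial response (PR), very good partial response (VGPR) and complete response (CR) as defined in" Section 10.2. Section 11.1 pools CR, VGPR and PR, and its rule for opening Stage 2 asks for at least two confirmed responses at PR level or better among the first 20 patients. The final rule asks for at least 8 confirmed responses among 35.

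The bands are in Section 10.2a:
- VGPR: "A VGPR is defined as the difference between involved and uninvolved FLCs [dFLC] < 4.0 mg/dL"
- PR: "Partial Response is defined as a dFLC decrease of ≥ 50%, but remaining > 4.0 mg/dL"
- CR is defined separately, by a normal free light chain ratio and negative serum and urine immunofixation.

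Under Section 10.2c, "Patients who do not meet criteria for objective response or progression" are classed as stable disease. On confirmation, Section 10.2 says only this: "Confirmation must be made by verification on two consecutive determinations". It does not say whether the two determinations must fall in the same category, or whether a better category confirms a lesser one.

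**The concern.** PR and VGPR should meet at 4.0 mg/dL, because the endpoint counts everything from PR upward. As printed they do not meet, since both exclude 4.0. A patient at that value with a large fall is scored below a patient with a slightly smaller fall. Because confirmation needs consecutive determinations, one such reading also interrupts a run of qualifying results. At stake is the classification of individual patients in a trial whose two decisions rest on counts of 2 and 8.

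**Working it through.** **Inputs.** The PR, VGPR and stable-disease rules come from Section 10.2. The entry floor for the light chain difference is 4.5 mg/dL (Section 5.1c). The design is 20 + 15 patients, stopping at one or fewer responses in 20, with success at 8 or more of 35 and rates of 10% against 30% (Section 11.1). The stated significance level is 2% and power 87% (Section 11.2a).

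**Step 1: reproduce the stated design.** The probability of success is the sum over x = 2 to 20 of P(X1 = x | 20, p) × P(X2 ≥ 8 − x | 15, p).
- p = 0.10: 0.0199, stated as 2%.
- p = 0.30: 0.8664, stated as 87%.

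Both figures reproduce.

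**Step 2: apply the bands as written.** Baseline 20.0 mg/dL, CR not met:

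| dFLC | Fall | PR (≥ 50% and > 4.0) | VGPR (< 4.0) | Category |
|---|---|---|---|---|
| 10.0 | 50.0% | yes | no | PR |
| 4.1 | 79.5% | yes | no | PR |
| 4.0 | 80.0% | no | no | stable disease |
| 3.9 | 80.5% | no | yes | VGPR |

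The classification goes response, non-response, response as dFLC falls.

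**Step 3: who can be affected.** A reading of 4.0 is a fall of (B − 4.0)/B from baseline B. This is at least 50% when B ≥ 8.0: (8.0 − 4.0)/8.0 = 50%. Below that baseline, 4.0 is a smaller fall (33.3% from 6.0, 11.1% from 4.5), so it is not a response under either band in any case. The gap concerns baselines of 8.0 mg/dL or more.

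**Step 4: effect on confirmation.** Baseline 20.0, consecutive readings, CR not met:

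| Readings | Categories as written | Confirmed as written? | If 4.0 counts as PR |
|---|---|---|---|
| 4.6, 4.0 | PR, stable | no | yes, at reading 2 |
| 4.6, 4.0, 3.7 | PR, stable, VGPR | no | yes, at reading 2 |
| 4.6, 4.0, 3.7, 3.5 | PR, stable, VGPR, VGPR | yes, at reading 4 | yes, at reading 2 |

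These results are the same whether confirmation means the same category twice or PR or better twice, because stable disease is no response on either reading. The fourth reading in the last row shows that a patient who stays on study usually recovers the confirmation.

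**Step 5: how often one patient decides the trial.** These are exact binomial probabilities for the stated design; the 25% and 20% rates are illustrative.

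| True rate | Exactly 2 of 20 at Stage 1 | Passes Stage 1 and ends on exactly 8 of 35 |
|---|---|---|
| 30% | 2.8% | 10.1% |
| 25% | 6.7% | 15.1% |
| 20% | 13.7% | 14.5% |

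The last column is the sum over x = 2 to 8 of P(X1 = x | 20, p) × P(X2 = 8 − x | 15, p). In such trials the loss of one responder reverses the decision. These figures describe how close the decision is. They do not give the chance that the 4.0 gap causes a loss.

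**The case against.** The strongest reply is that this is a single boundary value. The study calendar (Section 9.0) has serum free light chains every 28-day cycle for up to 24 cycles, and again off treatment before progression, so one reading of 4.0 will rarely settle a patient's best confirmed response. The documents do not state the reporting precision, and finer reporting makes an exact 4.0 rarer. This stands, and it is why the effect is small.

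A typographical cause is also possible. Section 10.3d prints an underlined greater-than sign before its 650 pg/mL threshold, so the PR limit may have been meant to include 4.0. That argument is weak, because the same PR sentence prints ≥ for the 50% condition.

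A reader might go further and infer that a PR which deepens to VGPR, for example 4.6 then 3.5 mg/dL from a baseline of at least 9.2 (half of 9.2 is 4.6), is unconfirmed because neither category is met twice. The documents do not support that. Section 10.2 does not require the same category on both determinations, and Section 11.1 attaches confirmation to the pooled endpoint. The natural reading is that PR followed by VGPR confirms. What remains is that no sentence says so outright.

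Nor is there a basis for a figure for lost power. The documents give no dFLC distribution, assay variation or early-stopping rate for responders. A delay in confirmation does not by itself move time to response, which Section 10.5 dates from first documentation.

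**Conclusion.** The gap at 4.0 mg/dL is real on the printed text and holds for any baseline of 8.0 mg/dL or more when CR is not met. It conflicts with Sections 1.1 and 11.1 and can break a consecutive pair on either reading of the confirmation rule. The effect is small and runs in the conservative direction: responders can be missed but not added, so the false-positive rate cannot rise. The sample size, the 2% significance level and the 87% power are correct as stated. It is worth correcting because the defect lies in the primary endpoint definition, the decision counts are small, and settling the category of such a patient after results are known is undesirable in an open-label single-arm trial. The conclusion rests on the printed inequalities; if the master copy shows the PR limit as inclusive, the gap disappears. Confirmation across categories needs clarifying but is not an error.

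**What to change.** In Section 10.2a, define PR as a dFLC decrease of at least 50% that does not meet VGPR or CR. This closes the gap without moving the VGPR limit.

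In Section 10.2, add as a clarification that the primary endpoint is confirmed when two consecutive determinations each show PR or better, whatever the category. This matches Section 11.1.

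The cost is two wording changes. No new data, tests or patients are needed, and the decision rules and stated operating characteristics stay as they are. The changes should be in place before responses are counted for Stage 1.
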